The total duration of this randomized, double-blind, placebo-controlled trial will be 2 years. For each participant the total duration of the study will be 14 weeks, including 8 weeks of intervention with SXB or PBO, preceded by a 4-week period of collection of baseline data, and followed by a 2-week period of data collection post-intervention. Subjects taking MLT or any other medication capable of affecting RBD other than clonazepam (CLZ) will maintain their regimen at fixed dose throughout the 14-week duration of the study. Those taking CLZ will proceed to reduction and discontinuation of CLZ, followed by a 2-week washout period prior to receiving study drug. If unable to discontinue CLZ prior to study drug, they will reduce CLZ to lowest acceptable dose by the end of the 4-week baseline period followed by cross-taper with SXB during the first 2 weeks of flexible dosing.

In each arm, dosage of SXB and PBO will be titrated up weekly (this weekly titration will occur via phone calls by the PI on days 2-6 after each new dose change) by up to 1.5g nightly dose increments from an initial 4.5g total nightly dose (which could be given

in two unequal doses if needed, or one single dose no greater than 4.5g) to an optimal individual dose based on clinical response on RBD symptoms and tolerability, to a maximum nightly dose of 9g ("flexible dose" period lasting up to 8 weeks). The optimal dose for each participant will then be continued for at least 4 weeks ("stable dose").

Flowchart

MOCA: Montreal Cognitive Assessment

PSG: Polysomnography

CGI: Clinical Global Impression questionnaires

- **Day 1 (Visit #1 = Initial visit with research coordinator):**
 - Verification of inclusion and exclusion criteria
 - Enrollment (if not performed prior)
 - Physical Exam (MoCA,
 - PSQI, PHQ-9, GAD-7, SCOPA-AUT, Epworth sleepiness scale
 - provide RBD logs and sleep diary for the 14 following weeks, 2 blank Karolinska scales, and two actigraphy devices (Philips Actiwatch2) to be worn on dominant wrist and ankle for one month

- instructions on when to complete Karolinska scale #1 (Day 21-27, one hour after waking up the day prior to sleep study) from home
 - Instructions on clonazepam taper, when applies
 - pregnancy testing for female subjects of childbearing age, when applicable
 - collection of adverse events (AEs)
 - MD (PI, coPI) will be available as needed via telephone or remote video conference system

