Our study will include a mixed group of participants, some with a neurological diagnosis of PD and some otherwise healthy individuals. We identify risk of dizziness and falls as the most concerning risk in patients with a diagnosis of synucleinopathy, as this could be aggravated by SXB. We will therefore carefully exclude from this study any participant who already suffers from balance impairment resulting in falls or requiring an ambulating device, as well as any patient with symptomatic orthostatic hypotension. Taken all these considerations into account, and given the expected interindividual variability regarding

optimal dose of SXB, we chose flexible dosing for highest clinical benefit while minimizing the risk of side effects.

The total amount of SXB for the 12 participants randomized to active drug is: 5,292g.
The total amount of PBO for the 12 participants randomized to placebo drug is: 5,292g.

Option for “Rescue” Open Label Extension Period

All participants, should they decide to drop out of the study, may become eligible for a “Rescue” open label extension period, during which they will receive open label active drug sodium oxybate in an unblinded fashion. This will provide patients the opportunity of experiencing benefit from the study drug. Such participants would then receive ascending doses of sodium oxybate, according to the protocol, and will also be asked to present for visits and second polysomnography starting at visit 2, otherwise required by the protocol until the end of the study.

Inclusion Criteria

- Adult patients aged 40 to 85 years
- Women may be included only if they have a negative β -HCG test at screen; are sterile (documented hysterectomy, bilateral oophorectomy, or bilateral salpingectomy, or congenitally sterile) or postmenopausal (no menses for 12 months without alternative medical cause).
- Women with childbearing potential whose male partners are potentially fertile must use one of the following highly effective birth control methods for the duration of the study (ie, starting at screening) and for 30 days after last dose of study drug
 - estrogen-progestin oral contraceptive pills, patches, or vaginal ring
 - progestogen pills, implant or injection
 - intrauterine device (IUD)
 - intrauterine hormone-releasing system (IUS)
 - bilateral tubal occlusion
 - vasectomised partner (the sole sexual partner who has received medical assessment of the surgical success)or
 - abstain from heterosexual intercourse

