- In individuals without a diagnosis of Parkinson's disease (PD), PSG-confirmed “definite RBD” per the International Classification of Sleep Disorders, 3rd edition (ICSD-3)
- In individuals with a diagnosis of PD, either PSG-confirmed diagnosis of RBD ("definite RBD") or history of dream-enactment ("probable RBD")
- RBD episodes ≥ 2 /week or ≥ 8 /month (defined as vocalization and/or limb or body movements attributed to dream-enactment)
- Reliable reporting by bed witness in the absence of patient awareness

Exclusion Criteria

- History of falls during ambulation in the last 6 months despite adequate neurologic treatment
- Requirement of an ambulatory device at home
- Inadequately treated symptomatic orthostatic hypotension (syncopal episode in the last 6 months)
- BMI > 35
- Untreated or uncontrolled OSA (4% desaturation AHI>15)
- Liver impairment
- Renal impairment
- Congestive heart failure
- Uncontrolled hypertension
- Treatment with valproic acid
- Current history of NREM parasomnias or parasomnia overlap syndrome (at least 2 episodes in the last 6 months)
- Diagnosis of narcolepsy
- Cognitive impairment resulting in inability to comply with treatment instructions
- Diagnosis of any dementia including dementia with Lewy bodies
- Diagnosis of multiple system atrophy
- RBD attributed to a CNS lesion
- PD Hoehn and Yahr stage 4 and 5
- Any change of PD regimen during the study period
- Current alcoholism or prior history of drug abuse
- Pregnancy
- Epilepsy currently treated with sedating antiepileptic drugs;
- Concomitant use of other CNS depressants, including but not limited to opioid analgesics, benzodiazepines other than clonazepam, muscle relaxants, and/or illicit CNS depressants
- Current depression (at least PHQ-9 score = 10), history of psychosis
- Any change of antidepressant regimen during the study period
- Chronic severe RLS (iRLS>20) (at least 3 days per week)
- Succinic semi-aldehyde dehydrogenase deficiency (SSADH)

Primary Endpoint

- Number of RBD episodes in one month (RBD log), last month of treatment compared to 1-month baseline

Secondary Endpoints

- Severity of RBD episodes in one month (RBD log), last month of treatment compared to 1-month baseline. Severity is scored from 1 to 3 (1: least severe, 3 most severe):

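### The listed orthostatic hypotension exclusion turns on recent syncope, so it can admit symptomatic patients whom the protocol's own safety rationale says will be excluded

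*Protocol*

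**What the plan says.** Two current parts of the Protocol state the exclusion differently.

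- **Treatment Regimen (narrative).** The sponsor writes "We identify risk of dizziness and falls as the most concerning risk in patients with a diagnosis of synucleinopathy", adds that SXB could worsen it, and gives the response: the trial will exclude "any participant who already suffers from balance impairment resulting in falls" or needing a walking aid, "as well as any patient with symptomatic orthostatic hypotension". The orthostatic clause has no condition on treatment, syncope or time window.
- **Exclusion Criteria (list).** The matching item reads "Inadequately treated symptomatic orthostatic hypotension (syncopal episode in the last 6 months"). Separate items cover falls during ambulation in the last 6 months, need for an ambulatory device at home, any dementia including dementia with Lewy bodies, multiple system atrophy, and Parkinson's disease at Hoehn and Yahr stage 4 or 5.

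The list is the operative text: Visit 1 in the Flowchart section includes "Verification of inclusion and exclusion criteria". The same visit collects "PSQI, PHQ-9, GAD-7, SCOPA-AUT, Epworth sleepiness scale" and a physical examination. The SAP does not deal with eligibility.

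**The concern.** The narrative offers this exclusion as the answer to the risk it ranks highest. If the list is narrower, some of the patients the sponsor says it will keep out can be randomized and started on 4.5 g nightly, with titration up to 9 g, at ages up to 85. Someone relying on the narrative would believe these patients are protected. What is at stake is participant safety and consistent screening, not the estimate of treatment effect.

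**Working it through.** No arithmetic applies. The check sets the two statements side by side, asks how the parenthesis should be read, and then asks whether anything else closes the gap.

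**1. Who is excluded under each text**

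| Patient with orthostatic hypotension | Narrative | List, syncope as threshold | List, syncope as example |
|---|---|---|---|
| A. Controlled on treatment, no symptoms, no syncope in 6 months | Not excluded (not symptomatic) | Eligible | Eligible |
| B. Current dizziness or presyncope, no syncope in 6 months | Excluded | Eligible | Excluded if judged inadequately treated |
| C. Inadequately treated, syncope in the last 6 months | Excluded | Excluded | Excluded |

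The texts agree on A and C. They differ on B: outright under the threshold reading, and at the investigator's discretion under the example reading.

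**2. Which reading is natural**

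Leaving aside the orthostatic item and one abbreviation, the exclusion list has five parentheses:

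- the apnea index, in "Untreated or uncontrolled OSA (4% desaturation AHI>15");
- the episode count, in "Current history of NREM parasomnias or parasomnia overlap syndrome (at least 2 episodes in the last 6 months");
- a PHQ-9 score of 10;
- an iRLS score above 20;
- a frequency of 3 days per week for restless legs.

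All five set a numeric cut-off for the condition beside them. A screener working down the list would probably treat the syncope parenthesis the same way. This is an inference from pattern. The syncope item contains no score and no explicit minimum count.

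**3. Whether other criteria catch patient B**

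- The falls and device items remove those whose hypotension has already led to falls (subject to that item's treatment qualifier) or to use of an aid. Patient B may have neither.
- Of the three synucleinopathies named in Scientific Basis/Rationale, dementia with Lewy bodies and multiple system atrophy are excluded, and Parkinson's disease is limited to stages below 4. Patient B may have earlier Parkinson's disease or isolated RBD.
- SCOPA-AUT is collected at Visit 1, but no listed criterion uses its score or an orthostatic blood pressure result. PHQ-9, from the same visit, does have a cut-off.

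**4. Whether monitoring substitutes for the exclusion**

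The weekly calls fall on days 2 to 6 after each new dose, and the dose can be lowered. Both act after the first exposure. The narrative promised exclusion before it.

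**The case against.** The strongest reply is that the conflict rests on one ambiguous parenthesis. If syncope is only an example, the investigator can judge that anyone still symptomatic is inadequately treated. The narrative makes the intent plain and would guide that judgment. This has force, and it is why the point is one of wording and not of a missing safeguard. It does not dispose of the matter. The threshold reading fits the rest of the list better, and Visit 1 is run by a research coordinator with a physician available by telephone or video as needed. A criterion for the top-ranked risk should not need interpretation there.

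Three stronger readings are tempting, and the documents do not support them.

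- **The treatment qualifier is itself a gap.** A reader might infer that patients with treated hypotension slip through. But the narrative excludes symptomatic disease. A patient controlled on treatment is arguably not symptomatic, and one still symptomatic is arguably inadequately treated. That qualifier is largely reconcilable with the narrative; the syncope parenthesis, as a threshold, is not.
- **The falls item needs the same rewriting.** A reader might want it tied to balance impairment, as in the narrative. The listed item already covers ambulatory falls of any cause, so that change would admit some fallers now excluded. The list is narrower only in counting falls that occur despite adequate neurologic treatment.
- **Baseline orthostatic readings are absent.** The available text of the Visit 1 examination line breaks off, while Visit 3 lists orthostatic vital signs. Whether a reading is taken at Visit 1 is not known, and nothing here depends on it.

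**Conclusion.** The point stands in limited form. Read as a threshold, the listed criterion does not enforce the exclusion that the narrative states. The gap is patients with current orthostatic dizziness or presyncope but no syncope in the last 6 months. Other criteria reduce this group without closing the gap.

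Its size cannot be stated. The plan assigns 12 of 24 participants to SXB, and the rescue option may give open-label SXB to participants who drop out of either arm, but no prevalence of such hypotension is given. A reader might assume one and calculate a risk. With prevalence p, the chance of at least one such patient among 12 is 1 − (1 − p)^12, which is 1 − 0.95^12 = 0.46 at 5% and 1 − 0.80^12 = 0.93 at 20%. Those results only restate the assumption. They also apply it uniformly to a group that the narrative describes as mixed, with some participants otherwise healthy. They should carry no weight.

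The conclusion rests on two assumptions: that the list governs screening, and that the parenthesis works as a threshold. If it is only an example, what remains is an ambiguity that still merits clarification. Sample size, power and the planned analysis are not affected.

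**What to change.** Replace the listed item with: *Symptomatic orthostatic hypotension (current orthostatic symptoms despite any treatment, or syncope attributed to it in the last 6 months).* This excludes patients B and C in the table and leaves patient A eligible.

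Leave the falls item as it is or, at most, delete its qualifier about adequate neurologic treatment. Do not restrict it to balance impairment.

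If the sponsor does mean to enrol symptomatic patients without recent syncope, the Treatment Regimen text should say so and justify it against the risk ranked highest there.

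The cost is the rewording of one criterion and probably a few more screen failures, whose number is unknown without a prevalence. No change to the SAP is needed.

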
Taken together, this suggests that SXB may be a viable treatment option in patients with isolated RBD or RBD associated with PD, who have failed MLT and CLZ due to lack of efficacy or intolerance.

Hypothesis

We hypothesize that nightly dose of SXB will result in reduction of RBD severity and frequency per patients report and objective polysomnographic and actigraphic (wrist-worn device) measures, over an 8-week double blind intervention comparing SXB and placebo (PBO). Additionally, we hypothesize that SXB improves sleep quality, and

reduces daytime sleepiness in subjects with RBD associated with a neurodegenerative condition.

Primary Objective

1. Reduction in RBD episodes frequency and severity (RBD log)

Secondary Objectives

1. Improvement in clinical global impression scores per patient and clinician (CGI- efficacy scale, CGI-E, and CGI-impression scale, CGI-I, respectively)
2. Reduction of RWAi by PSG
3. Reduction in movements severity and frequency during REM sleep by quantitative video-PSG analysis¹⁶
4. Changes in overall subjective sleepiness by Epworth sleepiness scale (ESS) and one hour after rise time by Karolinska scale
5. Tolerance and side effects to SXB and PBO

Exploratory Objectives

1. Reduction in "activity score" and "activity index" as measured by actigraphy¹⁷
2. Reduction in periodic limb movement (PLM) arousal index
3. Improved sleep quality by Pittsburgh Sleep Quality Index (PSQI)
4. Effects on mood measured by PHQ-9
5. Effects on anxiety measured by GAD-7
6. Effect on orthostatic heart rate and blood pressure (response to orthostatic maneuver)

[figure not shown]
Trial Design

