- **Day 1-28 (phone calls, weekly, when applicable):** guidance on downtitration of CLZ
- **Day 28 ± 7 days:** 1st video-PSG wearing home actigraphy device (Philips Actiwatch2) and additional wrist and ankle high-frequency actigraphy device (Xiaomi Amazfit Arc)
- **Day 29 (One day after Day 28 ± 7 days, Visit #2 = Randomization visit with research coordinator):**
 - Collection of 1-month RBD log and sleep diary
 - Collection of Karolinska scale #1
 - Collection of all actigraphy devices
 - Epworth sleepiness scale
 - Randomization
 - Subjects receive SXB or PBO and instructions on titration schedule
 - pregnancy testing for female subjects of childbearing age, when applicable
 - collection of adverse events (AEs)
 - MD (PI, coPI) will be available as needed via telephone or remote video conference system

Day 30-84 ± 7 days (phone calls): Every week after each new dose the subject will be called (including when the dose will remain stable), these phone calls will be made between day 2-6 to discuss response, record adverse events, and determine the next weeks titration dose.

- **Day 57-85 ± 7 days (Visit #3 = Interim visit with research coordinator):**
 - Collection of 1-month RBD log and sleep diary
 - Epworth sleepiness scale
 - PSQI, PHQ-9, GAD-7
 - Completion of CGI-E by participants
 - Completion of CGI-I by clinician
 - Physical Exam (including MoCA, orthostatic vital signs)
 - instructions on when to complete Karolinska scale #2 (Day 78-84, one hour after waking up the day prior to sleep study) from home
 - Participants provided with two actigraphy devices (Philips Actiwatch2) to be worn on dominant wrist and ankle for one month
 - pregnancy testing for female subjects of childbearing age, when applicable

- Collection of AEs, side effects
- MD (PI, coPI) will be available as needed via telephone or remote video conference system

- **Day 84-112 ± 7 days: 2nd video-PSG wearing home actigraphy device (Philips Actiwatch2) and additional wrist and ankle high-frequency actigraphy device (Xiaomi Amazfit Arc)**

- **Day 85-113 (One day after Day 84-112 ± 7 days, Visit #4 = Final Visit with research coordinator):**
 - Collection of high-frequency actigraphy device (Xiaomi Amazfit Arc)
 - Collection of 1-month RBD log and sleep diary
 - Collection of AEs, side effects
 - Collection of Karolinska scale #2
 - Epworth sleepiness scale
 - PSQI, PHQ-9, GAD-7, SCOPA-AUT
 - Completion of CGI-E by participants
 - Completion of CGI-I by clinician

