 1. non injurious behaviors: facial expressions, non-aggressive vocalizations (mumbling, gentle talking, casual conversation, singing, laughing...), twitches, gentle shaking, non-aggressive movements of fingers, arms or legs...;

2. potentially injurious: punching, kicking, arm flailing or thrashing around, at least one limb or head out of bed, sitting up in bed, crawling, attempting to stand up or leave bed, near falls, cursing, screaming, shouting, yelling, or any behavior requiring bed partner to wake up participant;
 3. injurious: any contact with bed partner (hitting or grabbing), wall or furniture, any fall or leaving bed (doving out, walking, jumping).
- CGI efficacy scale (CGE-E): 4-point therapeutic effect scale and 4-point side effect scale, jointly filled by patient and partner on last day of treatment
 - CGI improvement scale (CGI-I): 7-point improvement scale filled by clinician on last day of treatment
 - RWAi according SINBAR criteria comparing PSG pre-intervention to PSG post-intervention
 - video-PSG analysis of REM related vocalizations and movements (“simple” versus “complex”) as per Sixel-Döring and colleagues¹⁶
 - Sleep outcomes: EDS, Karolinska 1 h after awakening

Exploratory Endpoints

- “Activity index” as recorded by actigraphy¹⁷ (percentage of 30-second epochs with an activity score above zero) last month of treatment compared to 1-month baseline
- Sleep outcomes: PSQI
- Cognitive outcome: MoCA
- Mood and Anxiety: PHQ-9 and GAD-7
- Orthostatic vital signs

Sample Size Justification/Statistical Analysis

Sample size calculation was made for the outcome of number of RBD episodes per month. Based on the data published by Brunetti et al.¹⁸, the number of RBD episodes decreased from 11.2 \pm 5.2 at baseline to 10.3 \pm 3.7 per month in the placebo arm. To detect an effect size of 50% reduction in the number of RBD episodes per month ([placebo-active]/placebo) with a power of 80% and alpha of 5%, the number of participants would need to be 10 per arm. Based on prior studies using SXB in subjects with PD, a conservative drop out rate of 15-20% could be anticipated^{14,15}, which would require to enroll at least 24 participants, i.e. 12 participants per arm.

Reporting to Jazz Pharmaceuticals

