Sodium Oxybate in Treatment-Resistant REM Sleep Behavior Disorder (RBD): A Randomized Placebo-Controlled Trial

Statistical Analysis Plan

NCT04006925

January 11, 2023

Statistical analysis (using SAS 9.4, Cary, NC) was by intention-to-treat for the primary efficacy analysis, comparison of baseline characteristics, safety and tolerance and per-protocol (PP) for secondary/exploratory analyses. PP analysis included all participants who completed titration and the 4-week treatment period. Sample size calculation was based on a prior randomized controlled study by Brunetti et al.²⁵ To detect an effect size of 50% reduction in the number of RBD episodes per month ([placebo - active] / placebo) with a power of 80% and alpha of 5%, the number of participants needed to be 10 per arm. Anticipating a dropout rate of 20%, 24 participants required to be enrolled.

We tested the primary hypothesis that SXB is superior to placebo in reducing the number of RBD episodes from baseline, as observed in the last month of treatment using linear mixed effects models with random intercepts. Models were parameterized in two ways to estimate separate group trajectories and between-group differences in change over time. Cohen's d was calculated as a measure of treatment effect size. Similar hypotheses were tested on secondary and exploratory outcomes. Within- and between-group differences were assessed with paired- and unpaired t-tests, or with the Wilcoxon Signed Rank and Mann-Whitney U tests for nonnormal data. Bootstrapped percentile-based 95% confidence intervals were calculated based on 10,000 randomly resampled datasets. Participants scoring below 4 on the CGI-I and CGI-E were classified as "responders"; chi-square tests were performed to compare the proportion of responders between groups. All statistical tests were conducted using a 2-sided alpha level of 0.05. For secondary/exploratory analyses, bootstrapped percentile-based 95% confidence intervals were calculated based on 10,000 randomly resampled datasets. Descriptive statistics on safety data are provided for all randomized participants (intention-to-treat), by treatment group and study phase.

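### PHQ-9 of 10 or more defines depression at entry, but on treatment PHQ-9 is analysed only as an exploratory group comparison in completers, so a participant who crosses the cut-off and then stops is left out of the mood result

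*Protocol*

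**What the plan says.** - **Entry.** Protocol, Exclusion Criteria: "Current depression (at least PHQ-9 score = 10), history of psychosis". Participants therefore enter with scores of 0 to 9.
- **Measurement.** Protocol, Flowchart: Visit 1 (Day 1) lists "PSQI, PHQ-9, GAD-7, SCOPA-AUT, Epworth sleepiness scale". Visits 3 and 4 both list "PSQI, PHQ-9, GAD-7". PHQ-9 is not listed at Visit 2 (randomisation) or Visit 5 (follow-up).
- **Status on treatment.** Protocol, Exploratory Objectives: "Effects on mood measured by PHQ-9". Protocol, Exploratory Endpoints: "Mood and Anxiety: PHQ-9 and GAD-7". Neither entry gives a threshold or a shift category.
- **Analysis.** The SAP does not name PHQ-9. As an exploratory outcome it falls under "per-protocol (PP) for secondary/exploratory analyses", and the set is defined thus: "PP analysis included all participants who completed titration and the 4-week treatment period". The methods are the mixed models used for the primary outcome and the following: "Within- and between-group differences were assessed with paired- and unpaired t-tests", or rank tests for non-normal data, with bootstrap intervals. The only outcomes that the SAP dichotomises are CGI-I and CGI-E.
- **Safety.** The SAP describes safety data for every randomised participant, by group and phase. The protocol collects adverse events at visits and at weekly calls during treatment. Neither document places PHQ-9 in the safety data or ties a score of 10 or more to an adverse event.
- **Rescue.** Under the protocol's section on the rescue open-label extension, participants who drop out may receive open-label SXB and are asked to attend the later visits.

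**The concern.** The protocol sets a line on an instrument at entry and repeats the instrument on treatment, yet no planned table says how many people cross that line. Two features of the planned analysis can hide a crossing. A group average dilutes a change confined to a few participants. The completer set removes anyone who worsens and then stops, along with any Visit 3 score already collected.

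What is at stake is how the mood result reads. It could show no change, or even improvement, while some randomised participants had scores at which the protocol would not have enrolled them.

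**Working it through.** **The plan's own figures.** The documents give none for PHQ-9. The group sizes used below come from the sample size for RBD episodes. A 50% reduction from 10.3 is 5.15 episodes; with SD 3.7, two-sided alpha 0.05 and 80% power, a two-sample t-test needs 9.17, that is 10 per arm. At 15% dropout, 10/0.85 = 11.8, that is 12 per arm. The stated 10 per arm and 24 in total reproduce at these inputs. They have no further bearing on this point.

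Everything below rests on assumed PHQ-9 changes or crossing rates.

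**1. Loss through the completer set.** Suppose that in a 12-person arm two participants rise by 7 points and ten fall by 1.
- All 12: (2 × 7 − 10 × 1)/12 = 4/12 = +0.33.
- If the two are the non-completers: (10 × −1)/10 = −1.0, an apparent improvement.

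Dropout need not be related to mood. If two of 12 cross and two of 12 drop out at random, the chance that the completer set keeps both crossers is C(10,2)/C(12,2) = 45/66 = 0.68. It misses at least one with probability 0.32, and more often if low mood leads to stopping.

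**2. Loss through averaging.** Suppose that two of 12 SXB participants rise by 8 points and nobody else changes on average, with an SD of change of 2, 2.5 or 3.
- Mean difference: 2 × 8/12 = 1.33 points.
- Simulation (20,000 trials per SD): the between-arm t-test gives p < 0.05 in about 8 to 9% of trials, and the Mann-Whitney test in about 7%.
- With the two participants removed, the t-test gives about 5%, which is the false-positive rate.
- With 10 per arm, 80% power needs a standardised difference of 1.325, that is 2.65, 3.31 or 3.97 points for the three SDs.

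**3. What a count can and cannot do.**
- On significance it is no better. For 2/12 versus 0/12, the two-sided Fisher p = 2 × C(12,2)/C(24,2) = 132/276 = 0.48. With none on placebo, 4/12 gives p = 0.093 and 5/12 gives p = 0.037.
- Its value is descriptive. At true crossing rates of 5%, 10% and 20%, the chance of seeing at least one crosser, 1 − (1 − rate)^n, is 46%, 72% and 93% among 12 randomised, against 40%, 65% and 89% among 10 completers.
- With no crossings, the one-sided 95% upper bound, 1 − 0.05^(1/n), is 22.1% for 0/12 and 25.9% for 0/10.

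**4. Limits set by the visit schedule.** Randomisation is on Day 29 and Visit 3 falls on Day 57 to 85. The first on-treatment score therefore comes 57 − 29 = 28 to 85 − 29 = 56 days later, before the visit window. A participant who stops sooner may have no double-blind score. The only listed pre-treatment score is from Day 1, before any clonazepam taper.

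**The case against.** **Depression is not named as a risk of SXB.** This stands. The protocol's Treatment Regimen section names dizziness and falls as the main worry, and mood is a neutral exploratory objective. A reader might infer that the plan overlooks a known harm; the documents do not support that. An exclusion criterion describes who enters and does not by itself oblige the SAP to count later crossings.

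**A safety route already exists.** This also stands. A reader might infer that new depression on SXB goes uncounted. Depression recorded as an adverse event is summarised for all randomised participants, including those who drop out. CGI-E also carries a side-effect scale. What is missing is narrower: a PHQ-9 score of 10 or more does not itself enter any table.

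**The count is no more powerful than the mean.** Correct: Fisher p = 0.48 for 2/12 versus 0/12. A mean difference of 1.33 points is also 0.44 to 0.67 of the assumed SDs, so it is not negligible, and the SAP's bootstrap intervals mean that the reading does not rest on a p-value alone. The case for the row is that it is visible and includes all randomised participants with a score. It is not a case about detection.

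**A simple count could mislead.** A score at any visit after randomisation, tabulated by arm, could credit a placebo participant's score on open-label rescue SXB to placebo. The row must separate those scores. It would also treat a move from 9 to 10 like one from 4 to 12, so each crosser's Day 1 score is needed.

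**Nothing is irretrievably lost.** True. Scores collected at Visits 3 and 4 remain in the data, and a count could be made from them at any time.

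**Conclusion.** The point holds as a gap in reporting. On the text alone, PHQ-9 on treatment is analysed only by group comparison in completers, no count at the protocol's own cut-off is planned, and a participant who crosses it and then stops is left out of the mood result. This conclusion needs no assumed figures.

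Its size cannot be taken from the documents. Under the assumptions shown, dropping two crossers moves an arm's mean change from +0.33 to −1.0, and random dropout of two in 12 loses at least one of two crossers 32% of the time. Both figures depend on the assumed number of crossers and dropouts; the means also depend on the assumed size of the changes.

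The gap applies equally to both arms. It changes no sample size or alpha and affects no primary or secondary conclusion. It is a modest, inexpensive improvement to how tolerability is reported.

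**What to change.** Add one descriptive row to the SAP's all-randomised safety summary:

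- by randomised arm, the number with PHQ-9 of 10 or more at any assessment during double-blind treatment (Visit 3 or 4), including those who later stop;
- the denominator with at least one such score, and the number with none;
- each crosser's Day 1 score;
- scores taken during open-label rescue SXB listed separately and not counted under the randomised arm.

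Keep the mean PHQ-9 change as an exploratory analysis.

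The cost is one table row and a short listing, with no new assessment. The downsides should be stated beside it. With about 12 per arm the proportions are imprecise and no test is warranted. Early stoppers may have no score. Because PHQ-9 is not listed at Visit 2, a crossing cannot be dated to after the first dose and has to be read against placebo.
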